6.5.2. Prohibited Concomitant Therapy

Live vaccinations are not allowed up to 3 months prior to screening or at any time during the study. Live herpes zoster vaccination is not permitted within 30 days of planned randomization or at any time during the study.

Nonlive seasonal vaccinations and/or emergency vaccination, such as rabies or tetanus vaccinations, are allowed.

6.5.3. Standard of Care Therapy after Week 14

All placebo patients should begin SOC therapy at Week 14 at the investigator's discretion.

Participants randomized to LY3462817 at baseline and not achieving low disease activity (CDAI ≤ 10) at Week 14 will no longer receive study drug infusions and should receive SOC therapy at the investigator's discretion.

Participants who achieve low disease activity at Week 14, and maintain treatment with LY3462817 during Period 2, can be switched to SOC prior to Week 24 if the participant stops receiving clinical benefit. Name(s) and dosage regimen(s) must be recorded for the SOC therapy. Standard of care medications will not be supplied by the sponsor.

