8.9. Immunogenicity Assessments

All samples for immunogenicity should be taken predose when applicable at the visits and times specified in the SoA (Section 1.3). Venous blood samples will be collected and evaluated to determine antibody production against LY3462817. To interpret the results of immunogenicity, venous blood samples will be collected at the same time points to determine the concentrations of LY3462817. Antidrug antibodies may be further characterized for their ability to neutralize the activity of LY3462817.

Treatment-emergent antidrug antibody (TE-ADA) classifications are described in Section 9.4.6.

Sample retention is described in Appendix 1, Section 10.1.12.

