9.4.6. Evaluation of Immunogenicity

Treatment-emergent antidrug antibodies (ADAs) are defined as participants

- with a 2-fold (1 dilution) increase in titer than the minimum required dilution if no ADAs were detected at baseline (treatment-induced ADA) or

- with a 4-fold (2 dilutions) increase in titer compared with baseline if ADAs were detected at baseline (treatment-boosted ADA).

The frequency and percentage of participants with preexisting ADA and who are TE-ADA positive (TE-ADA+) to LY3462817 will be tabulated.

For the TE ADA+ participants, the distribution of maximum titers will be described. The frequency of neutralizing antibodies, if assessed, may also be tabulated for the TE-ADA+ participants.

The relationship between the presence of antibodies and LY3462817 concentrations and PD response, including safety and efficacy, may also be assessed. Additional details may be provided in the SAP.

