1.2. Study Design

This is a Phase 2, proof-of-concept, placebo-controlled, double-blind, randomized study in adult participants with moderately to severely active RA who have had an inadequate response to csDMARDs, or to bDMARDs/tsDMARDs. Participants will be administered LY3462817 or placebo IV Q4W.

Screening Period (Visit 1, Days -42 to -1)

Participants will sign the informed consent document(s) at Visit 1, prior to completion of any procedures. Participants will be evaluated for study eligibility ≤ 42 days prior to the baseline visit (Visit 2).

Period 1: Double-blind Treatment (Visits 2 to 6; 12 weeks)

At the baseline visit (Visit 2), participants who fulfill the eligibility criteria will be randomized to receive LY3462817 700 mg, LY3462817 300 mg, or placebo in an allocation ratio of 2:1:1. The double-blind treatment period will establish the clinical efficacy and safety of LY3462817. The study will be evaluated for the primary objective at the end of the double-blind treatment period.

Period 2 (Visits 6 to 10; 12 weeks)

In Period 2, all subjects will receive LY3462817 to assess safety and tolerability data and explore clinical activity with additional dosing. At Week 14, participants will be evaluated for clinical benefit.

Posttreatment Safety Follow-up Period (Visits V801 and 802; 12 weeks)

Following Period 2, participants will be followed posttreatment for 12 weeks to assess safety, study drug exposure, and clinical disease activity measures.

2. Statistical Hypotheses

For the primary estimand with primary endpoint, change from baseline to week 12 in DAS28-CRP, the following 2 (confirmatory) 1-sided hypotheses are planned to be tested for LY3462817 700 mg versus placebo. Let the mean treatment difference be defined as $\mu = (\text{LY3462817 700 mg} - \text{placebo})$.

$H_0: \mu \geq 0.0$ against $H_a: \mu < 0.0$

Operationally the hypotheses will be evaluated by 2-sided tests.

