4.6.4.4. Immunogenicity

The frequency and percentage of patients with positive anti-drug antibodies (ADAs) by visit will be summarized by treatment arm. The frequency and percentage of patients with positive ADAs

at any time point during the Treatment Period (including pre-treatment visits) up to and including Visit 9 (Week 24) will also be summarized by treatment arm.

The frequency and percentage of patients with a treatment-emergent positive ADA incidence will be summarized by treatment arm. A treatment-emergent incidence is defined as a four-fold increase [2 dilution increase] in immunogenicity titer over the baseline titer during the Treatment Period. Scheduled visits, unscheduled visits, and repeat measurements will be included.

The time to the development of treatment-emergent ADAs will be calculated as:

Time to development of treatment-emergent ADAs (in weeks) = (Date of development of treatment-emergent ADAs – Date of randomization + 1) / 7.

If a patient has not developed treatment-emergent ADAs, they will be censored at the date of the last immunogenicity assessment during the Treatment Period. If they did not have an immunogenicity assessment, they will be censored at the date of first injection.

The time to development of treatment-emergent ADAs will be analyzed using a Cox proportional hazards model, with treatment arm and strata (previous RA therapy population) fitted as explanatory variables. The estimated hazard ratio, 95% confidence interval and p-value for treatment comparisons between each LY dose and placebo will be presented. A Kaplan-Meier plot of the time to development of treatment-emergent ADAs will be presented by treatment arm.

The frequency and percentage of patients with both a treatment-emergent positive ADA incidence (yes, no) and at least one treatment-emergent Hypersensitivity adverse event (yes, no) will be summarized by treatment arm. Similarly, the frequency and percentage of patients with both a treatment-emergent positive ADA incidence (yes, no) and at least one treatment-emergent injection site reaction (yes, no) adverse event will be summarized by treatment arm.

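### SAP 4.6.4.4 plans Cox hazard ratios for anti-drug antibodies against a placebo arm that, under the current protocol, never receives the drug; at low background positivity they probably have no finite estimate, and no fallback is named

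*SAP*

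**What the plan says.** SAP 4.6.4.4 analyses time from randomization to TE-ADA with a Cox model, "with treatment arm and strata (previous RA therapy population) fitted as explanatory variables". It then states: "The estimated hazard ratio, 95% confidence interval and p-value for treatment comparisons between each LY dose and placebo will be presented". Participants without the event are censored at their last immunogenicity assessment in the Treatment Period, which SAP 4.1 defines as Periods 1 and 2 together. The section also tabulates TE-ADA frequency and percentage by arm and plans a Kaplan-Meier plot by arm. It gives no rule for an arm without events and does not say whether inference is Wald, likelihood-ratio, exact or penalised.

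The protocol is more modest. Section 8.9 says: "Venous blood samples will be collected and evaluated to determine antibody production against LY3462817". Section 9.4.6 says: "The frequency and percentage of participants with preexisting ADA and who are TE-ADA positive (TE-ADA+) to LY3462817 will be tabulated". It adds titer distributions and possible relationships with concentration and response, but no Cox model. SAP 4.9 reports no change to protocol-planned analyses.

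Two pairs of passages disagree:
- **Exposure in Period 2.** Protocol 6.5.3: "All placebo patients should begin SOC therapy at Week 14". Protocol 4.1 agrees: only participants assigned to LY at baseline can continue on it. SAP 1.2: "In Period 2, all subjects will receive LY3462817 to assess safety and tolerability data and explore clinical activity with additional dosing".
- **The event.** SAP 4.6.4.4: "A treatment-emergent incidence is defined as a four-fold increase [2 dilution increase] in immunogenicity titer over the baseline titer during the Treatment Period". Protocol 9.4.6 keeps a four-fold rule for participants with antibodies at baseline and has a separate criterion for the others: "with a 2-fold (1 dilution) increase in titer than the minimum required dilution if no ADAs were detected at baseline".

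**The concern.** Placebo is saline (Protocol 6.1). If that arm never meets the drug, its TE-ADA count is assay background plus titer changes in participants who already had reactive antibodies. In an arm of about 20 that count may well be zero. A Cox model with an empty reference arm has a partial likelihood that keeps rising as the hazard ratio grows, so there is no maximum to report. Software then stops at an arbitrary large value with a huge standard error, and the Wald p-value drifts towards 1. A table built on that output could read as no difference in immunogenicity when every event was on active drug. If the gap is noticed only after unblinding, the substitute method would be chosen with the data in view.

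**Working it through.** The documents give no TE-ADA rate, event count or hazard ratio for this analysis, so there is no planned figure to reproduce. All rates below are assumptions, shown over a range.

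**Inputs.** Arm sizes are about 40 (700 mg), 20 (300 mg) and 20 (placebo), from Protocol 9.2. Post-baseline antibody samples to Week 24 fall at Weeks 4, 12, 16 and 24 (Protocol 1.3), with no distinction by arm.

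**1. Chance of an empty placebo arm, placebo never exposed.** With per-participant background rate b by Week 24, P(no placebo event) = (1 − b)^20.

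| b | 0% | 1% | 2% | 5% | 10% |
|---|---|---|---|---|---|
| P(no event in 20) | 100% | 82% | 67% | 36% | 12% |

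A non-finite 700 mg ratio also needs at least one event among the 40. At a true LY rate of 10% and no background that has probability 1 − 0.9^40 = 0.985, and more at higher rates. So the table is close to the chance of a non-finite ratio. A simulation with LY rates of 10 to 40% gave 99–100%, 66–68%, 35–36% and 12–13% at b = 0, 2, 5 and 10%.

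**2. What the fit does.** Illustrative data: 8/40 events on 700 mg, 4/20 on 300 mg and k/20 on placebo. Event times are spread over the four sampling weeks and everyone else is censored at Week 24. Ties are handled by Breslow's method, with treatment terms only (the stratum is left out).

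With k = 0, the partial log-likelihood with both LY log hazard ratios set to 1, 2, 5, 10 and 15 is −49.67, −48.75, −48.20, −48.1748 and −48.1746. It rises to a plateau without a maximum. Newton-Raphson gives, for 700 mg:

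| Iteration | log HR | SE | Wald p |
|---|---|---|---|
| 5 | 4.5 | 4.6 | 0.33 |
| 10 | 9.5 | 55.6 | 0.86 |
| 15 | 14.5 | 677 | 0.98 |
| 25 | 24.5 | 100,508 | 1.00 |

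On the same data the likelihood-ratio p-value is 0.0085 and the profile-likelihood interval runs from 2.0 upward without limit. The reported conclusion would depend on which statistic is printed, and the SAP does not choose.

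With k = 1 the 700 mg ratio is 4.2 (Wald 95% CI 0.52 to 33). With k = 2 it is 2.0 (0.43 to 9.5). One background positive in the placebo arm halves the estimate.

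**3. The SAP 1.2 reading, placebo on LY from Week 12.** Assume a constant hazard from first exposure, with TE-ADA probability L over 24 weeks and no background. A placebo participant then has 12 exposed weeks, so P(no placebo event) = ((1 − L)^(12/24))^20 = (1 − L)^10. Multiplying by 1 − (1 − L)^40:
- L = 10%: 0.349 × 0.985 = 34%
- L = 20%: 0.107 × 1.000 = 11%
- L = 40%: 0.6%

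Simulation (5,000 trials per setting) gave 34%, 10% and 0.5%.

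The ratio is now usually finite, but it is not constant over time. Take L = 20% and b = 2%. Before Week 12 the LY-to-placebo hazard ratio is (−ln 0.80 − ln 0.98) / (−ln 0.98) = (0.2231 + 0.0202) / 0.0202 ≈ 12. After Week 12 both arms are exposed and it is 1. A single Cox ratio averages the two, with weights set by when events happen to be detected.

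**The case against.** The strongest reply is that only Wald inference fails, and the SAP does not name Wald. The likelihood-ratio test and a lower bound survive an empty placebo arm. Background rates are unknown, and at 5 or 10% the ratio is finite more often than not. Pre-existing antibodies are foreseen in Protocol 9.4.6, and the SAP applies its four-fold rule in every arm, so placebo events are possible. Under SAP 1.2 placebo is exposed. Protocol 9.4.6 lets the SAP add detail and 9.4.1 allows further exploratory analyses, so the Cox model breaches nothing. Immunogenicity is not a listed objective, and no interim rule depends on this ratio.

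Much of this stands, and it rules out several stronger readings that a reader might infer:
- That the ratio is always infinite or meaningless. It is non-finite only with no placebo events; otherwise it is a defined comparison of LY with background, though of little interest.
- That every placebo event is an assay false positive. A rise in a pre-existing antibody titer would also count.
- That no immunogenicity inference can be produced, or that incidence by dose is not estimated. Incidence by arm is already tabulated, and a one-sided bound would exist.
- That the documents agree placebo is never exposed. SAP 1.2 says otherwise.

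The reply does not rescue the analysis. A surviving test helps only if it is prespecified. The finite cases have intervals spanning a factor of 20 or more. The Period 2 reading replaces a likely empty reference arm with a comparison that breaks proportional hazards. SAP 4.6.1 also sits badly with SAP 1.2, since it limits its Period 2 exposure summaries to participants still on one of the two LY doses.

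**Conclusion.** The point holds in a conditional form. Under the current protocol, the planned hazard ratio against placebo has no finite estimate whenever placebo has no event and LY has at least one. With about 20 placebo participants, an empty placebo arm has probability 82% at 1% background and 67% at 2%, falling to 36% at 5% and 12% at 10%. These rates are assumed, so how likely the failure is depends on an assay property the documents do not give. Where the ratio is finite it is too imprecise to use: 4.2 (0.52 to 33) with one placebo event in the illustrative data. Under the SAP 1.2 description it is usually finite, but it mixes immediate with delayed exposure.

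The change is worth making because the stated analysis would probably give an unusable result if background is low, and the remedy is nearly free. It does not touch the primary efficacy conclusion.

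**What to change.** 1. Reconcile SAP 1.2 with Protocol 4.1 and 6.5.3 on who receives LY3462817 in Period 2. The meaning of any placebo comparison depends on it.
2. Reconcile the TE-ADA definition. SAP 4.6.4.4 has only the four-fold rule over baseline titer, which leaves unclear how participants with no antibodies at baseline become events; Protocol 9.4.6 has a two-fold criterion for them. Incidence in every arm depends on the choice.
3. Delete the Cox contrast of each LY dose with placebo. Add exact 95% intervals to the TE-ADA incidence already tabulated by arm, and report the placebo rate as a check on background. An empty placebo arm then still gives a usable statement: for 0/20 the exact upper limit is 1 − 0.025^(1/20) = 16.8%. Keep the Kaplan-Meier curve as description.
4. If a comparison with placebo is kept, prespecify an exact method, or Firth-penalised Cox regression with profile-likelihood intervals, before unblinding.

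Cost: the Cox change is one paragraph and reduces programming; items 1 and 2 are text corrections. The downside is that no model-based hazard ratio is reported for this endpoint.

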4.6.5. Vital Signs and Other Physical Findings

Vital signs and physical characteristics to be summarized include temperature, sitting heart rate, sitting blood pressure (systolic and diastolic), weight, and BMI. Vital signs and physical characteristics will be summarized by treatment arm for baseline, all post-baseline visits, Week 24 endpoint, and change from baseline to post-baseline visits and Week 24 endpoint.

Change from baseline to Week 24 endpoint in vital signs and physical characteristics will be summarized for patients who have both a baseline and at least one post-baseline result. Baseline is defined as the last non-missing result on or prior to the date of the first injection of study treatment.

Change from the minimum value on or prior to the date of the first injection of study treatment to the minimum value during the Treatment Period in vital signs and physical characteristics will be summarized for patients who have both a baseline and at least one post-baseline result. Similarly, change from the maximum value on or prior to the date of the first injection of study treatment to the maximum value during the Treatment Period in vital signs and physical characteristics will be summarized for patients who have both a baseline and at least one post-baseline result. Scheduled visits, unscheduled visits, and repeat measurements will be included.

The percentages of patients with treatment-emergent high or low vital signs and physical characteristics at any time during the Treatment Period will be summarized. Similarly, the percentages of patients with treatment-emergent high or low vital signs and physical

characteristics at Week 24 endpoint will be summarized. A treatment-emergent high result is defined as a change from a value less than the high limit at all baseline visits to a value greater than or equal to the high limit at any time during the Treatment Period. A treatment-emergent low result is defined as a change from a value greater than the low limit at all baseline visits to a value less than or equal to the low limit at any time during the Treatment Period. For each vital sign and physical characteristic, only patients who were normal (i.e., less than the high limit for treatment-emergent high, or greater than the low limit for treatment-emergent low) at all baseline visits and who have at least one non-missing post-baseline result will be included in the denominator when computing the percentages of patients with treatment-emergent high or low results. Scheduled visits, unscheduled visits, and repeat measurements will be included. Table 2 will be used to define the low and high limits.

A by-patient listing of all vital signs and physical characteristics during the Treatment Period will be provided. Additionally, a by-patient listing of treatment-emergent high or low vital signs and physical characteristics during the Treatment Period will be provided.

Table 2 **Selected Categorical Limits for Blood Pressure, Heart Rate and Weight**

Parameter	Low	High
Systolic BP (mm Hg) ¹ (supine or sitting – forearm at heart level)	≤ 90 and decrease from baseline ≥ 20	≥ 160 and increase from baseline ≥ 20
Diastolic BP (mm Hg) ¹ (supine or sitting – forearm at heart level)	≤ 50 and decrease from baseline ≥ 10	≥ 100 and increase from baseline ≥ 10
Heart Rate (bpm) ¹ (supine or sitting)	< 50 and decrease from baseline ≥ 15	> 120 and increase from baseline ≥ 15
Weight (kg) (consistent clothing and timing in relationship to meals and voiding)	(Loss) decrease from baseline ≥ 7%	(Gain) increase from baseline ≥ 7%

1. Chobanian, AV, et al., The JNC 7 Report, The seventh report of the Joint National Committee on Prevention, Detection, Evaluation, and Treatment of High Blood Pressure, *JAMA*, 289:2560(2003).

4.6.6. Electrocardiograms

For each patient, a single 12-lead digital ECG was collected according to the Schedule of Activities. ECGs had to be recorded before collecting any blood for safety or PK tests. Unscheduled ECGs could be obtained at additional times, when deemed clinically necessary.

Digital ECGs were electronically transmitted from the investigator sites to a central ECG laboratory designated by Lilly. A cardiologist at the central ECG laboratory conducted a full overread on ECGs (including all intervals). All data from the overreads were placed in the Lilly database for analytical and study report purposes.

Results for each ECG parameter will be summarized by treatment group at each visit for the observed data and for changes from baseline.

The overall ECG assessment as determined by the investigator will be reported as “Normal” or “Abnormal – not clinically significant”, or “Abnormal – clinically significant” and summarized by visit and across visits. A shift table of overall ECG assessment from baseline to the most extreme post-baseline value will be presented.

Additionally, the highest post-baseline value for QTc interval (using Fridericia’s correction) will be summarized descriptively as a categorical variable. Each QTcF value for a given subject will be grouped into 3 categories:

- QTcF interval ≥ 450 - <480 msec
- QTcF interval ≥ 480 - <500 msec
- QTcF interval ≥ 500 msec

The largest post-baseline change in QTcF measures will also be analyzed as categorical variables. The change in QTcF in a given subject will be grouped into 2 categories:

- QTcF interval increases from baseline ≥ 30 msec
- QTcF interval increases from baseline ≥ 60 msec

Relevant ECG data will also be displayed in separate listings for:

- Subjects who shifted from normal or abnormal not clinically significant at baseline to abnormal clinically significant during the treatment period
- Subjects who had an abnormal clinically significant assessment at any time during the study
- Subjects who ever had a QTcF interval increase from baseline ≥ 30 msec during the treatment period
- Subjects who ever had any value of QTcF interval ≥ 450 msec at any visit

4.6.7. Pregnancy

Any reported positive pregnancy results or reported pregnancies will be listed.

4.7. Other Analyses

4.7.1. Other variables and/or parameters

LY3462817 concentrations will be illustrated graphically and summarized descriptively. To facilitate the planning of future clinical studies, a model-based approach implemented using nonlinear mixed effects modeling (NONMEM) or other appropriate software may be conducted. Receptor occupancy and soluble PD-1 data over time will be summarized by dose level. Exploratory PK/PD analyses may be conducted to evaluate the relationship between LY3462817 exposure and selected measures of response (for example, RO, sPD-1, clinical endpoints, and/or biomarkers). As appropriate, data from the present study may be combined with data from other

studies in model-based analyses. Additional analyses may be conducted if deemed appropriate. Further details on PK and PK/PD analyses will be provided in the PK/PD analysis plan.

4.7.2. Subgroup analyses

Subgroup analyses of the primary endpoint will be made to assess consistency of the intervention effect across the following subgroups:

- previous RA therapy population (prior use of csDMARD only or prior tsDMARD/bDMARD use)
- gender
- race
- geographic region
- previous therapies,
- disease duration.

If the number of participants is too small (less than 10%) within a subgroup, then the subgroup categories may be redefined prior to unblinding the study.

A MMRM analysis will be used to analyze the subgroup analyses. The MMRM model will include treatment, strata (previous RA therapy population), subgroup, baseline value, visit, treatment-by-visit interaction, and treatment-by-subgroup in the model as fixed factors, and patient as a random factor. An unstructured covariance matrix will be used to model the within-subject errors. If this analysis fails to converge, other structures will be tested (in this order: Toeplitz, Autoregressive with heterogeneity, and Compound Symmetry). The Kenward-Roger approximation will be used to estimate denominator degrees of freedom.

For participants who discontinue study intervention and/or receive rescue therapy, post-discontinuation or post-rescue observations will not be included.

